12.1.5.1 Insufficient Data for Analysis/Presentation

If there are no values or events at the general value then the break out should not be presented. For example if the number of AEs related to study procedure is zero then the presentation by severity of related events will not be produced.

Some of the TFLs may not have sufficient numbers of subjects or data for presentation. If this occurs, the blank TFL shell will be presented with a message printed in the center of the table, such as, "No serious adverse events occurred for this study."

For categories of continuous data summaries that have <4 subjects no summaries will be shown.

12.1.6 Handling of Unplanned Data

Unscheduled post-product use readings will be excluded from the summary statistics. Unscheduled readings will be labelled as unscheduled in the listings and mapped to the relative study day using the date of the study day until midnight.

12.1.7 Multiple Comparisons / Multiplicity

The primary endpoints will be tested using a multiple testing procedure to preserve the overall alpha level by simultaneously testing the endpoints using a closed procedure with each test performed at an alpha level of 5%. This implies that statistical significance is required for all primary endpoints in order to be able to make confirmatory claims about any of the endpoints.

No adjustment will be made on any of the secondary endpoints.

12.2 Disposition of Subjects

A subject is considered:

- Enrolled if he/she was randomized or if not randomized he/she performed the product trial and he/she confirmed to be willing to use the product.

- Completed Confinement, Completed Day 30, Day 60, Day 90 Visits if he/she did not discontinue until the discharge at Day 6, Day 31, Day 61, and Day 91 respectively.

The number and percent of subjects will be summarized for the following categories: subjects screened, screening failures that tried product, screening failures that did not try product, enrolled subjects, enrolled and not randomized, randomized subjects, completed confinement, completed Day 30 Visit, completed Day 60 Visit, completed Day 90 Visit, completed study, and discontinued (if applicable discontinued subject that never used their allocated products will be identified).

Inclusion and exclusion criteria will be listed as to whether the subjects have met or not met the criteria.

All subjects who fail to complete the study will be categorized by their primary reason for discontinuation and summarized by randomization arm for the FAS. Disposition of subjects and reasons for discontinuation will also be summarized separately. Supportive listings will be provided.

The number and percent of randomized subjects with protocol deviations will be summarized by randomization arm for the PP Set and Safety Population broken down by main deviation category (major/minor), sub-categories and evaluability. Subjects will be counted once per deviation category, and can be counted for more than one deviation category.

The number and percent of randomized subjects included in each analysis population will be summarized by randomization arm for the Full Safety Population. For subjects excluded from the analysis populations this will be broken down by reason for exclusion. Subjects will be counted once per exclusion, and can be counted for more than one exclusion.

Supportive listing will be provided, including any additional comments for tests that are not performed to be included on the listings of individual data.

The data will be presented in the below outputs:

TFL number	Title
TABLES	
15.2.1.1	Summary of Subject Disposition – All Screened Subjects
15.2.1.2	Summary of Reasons for Discontinuations – FAS
15.2.1.3.1.1	Summary of Protocol Deviations – PP Set
15.2.1.3.1.2	Summary of Protocol Deviations – Safety Population
15.2.1.3.2	Analysis Sets and Reasons for Exclusion from Analyses – Full Safety Population

TFL number	Title
LISTINGS	
15.3.1.1	Listing of Inclusion/Exclusion Criteria
15.3.1.9	Listing of Subject Disposition, Randomization and Assignment to Analysis Sets
15.3.1.11	Listing of Protocol Deviations
15.3.2.3	Listing of Subjects and Observations Excluded from Analysis Populations
16.1.7	Listing of Randomization Schemes and Codes

12.3 Demographics and Other Baseline Characteristics

Demographic and baseline characteristics will be listed and summarized for the Safety Population, FAS and for the PP set in periods 1 - 4.

The demographic variables age, sex, race, body weight, height, BMI and waist circumference will be summarized by randomization arm, and by the two stratification factors (sex, and mCC consumption). Other baseline characteristics will also be included in the table.

No inferential analyses will be presented for the demographic and baseline characteristics.

The data will be presented in the below outputs:

TFL number	Title
TABLES	
15.2.1.4.1	Summary of Demographics and Other Baseline Characteristics – Safety Population
15.2.1.4.2	Summary of Demographics and Other Baseline Characteristics – FAS
15.2.1.4.3	Summary of Demographics and Other Baseline Characteristics – PP Set
15.2.1.4.3.1	Summary of Demographics and Other Baseline Characteristics by Sex – PP Set
15.2.1.4.3.2	Summary of Demographics and Other Baseline Characteristics by Cigarette Consumption – PP Set
LISTINGS	
15.3.1.8	Listing of Demographics

12.3.1 Current Cigarette Brand and Smoking Characteristics

The following smoking characteristics at Admission (Day -2) will be summarized and listed as specified in Section 12.3 “Demographics and Other Baseline Characteristics”: ISO tar yields (continuous and categorized as as 1-5 mg, 6-8 mg, 9-10 mg and >10 mg), ISO nicotine level (continuous and categorized as ≤ 0.6 mg and > 0.6 mg), and number of mCCs smoked (categorized as 10-19 cig/day and >19 cig/day). The summaries will be presented for the Safety Population, FAS and PP Set.

Current mCC brand(s) smoked by the subject and recorded at Screening will be summarized for the FAS. Only brands used by at least 4 subjects will be tabulated. An “other” category will contain all the brands used by less than 4 subjects. All the data at Screening and Admission (Day -2) will be listed by randomization arm and study day.

Smoking history, including whether subjects have smoked for at least the last three consecutive years and the subject’s mCCs consumption any during the previous 4 weeks will be listed by randomization arm at Screening and Admission (Day -2) where applicable

Data will be listed and summarized as presented in the below outputs:

TFL number	Title
TABLES	
15.2.1.4.1	Summary of Demographics and Other Baseline Characteristics – Safety Population
15.2.1.4.2	Summary of Demographics and Other Baseline Characteristics – FAS
15.2.1.4.3	Summary of Demographics and Other Baseline Characteristics – PP Set
15.2.1.4.3.1	Summary of Demographics and Other Baseline Characteristics by Sex – PP Set
15.2.1.4.3.2	Summary of Demographics and Other Baseline Characteristics by Cigarette Consumption – PP Set
15.2.1.5	Summary of Current Cigarette Brands At Screening – FAS
LISTINGS	
15.3.1.2	Listing of Current Cigarette Brands
15.3.1.3	Listing of Smoking History

12.3.2 Socio-Economic Status Questionnaire

Subject answers will be listed. The number and percentage of subjects in each category from each question apart from questions 5a and 5b will be summarized, and presented in listings as shown below. For question 5a the number and percent of subjects in categories 1-11, 12 and 13 will be presented and then the number and percent of subjects in each of the categories 1-11. For question 5b the number and percent of subjects who answered categories 12 or 13 from question 5a will be presented for categories 1-2, 3 and 4. In addition the number and percent of subjects in categories 1 and 2 will be presented. The summaries will be presented for the Safety Population, FAS and PP Set.

TFL number	Title
TABLES	
15.2.1.4.1	Summary of Demographics and Other Baseline Characteristics – Safety Population
15.2.1.4.2	Summary of Demographics and Other Baseline Characteristics – FAS
15.2.1.4.3	Summary of Demographics and Other Baseline Characteristics – PP Set
15.2.1.4.3.1	Summary of Demographics and Other Baseline Characteristics by Sex – PP Set
15.2.1.4.3.2	Summary of Demographics and Other Baseline Characteristics by Cigarette Consumption – PP Set
LISTINGS	
15.3.1.12	Listing of Socio-Economic Questionnaire Results

12.3.3 Medical History and Concomitant Diseases

Medical history is defined as any condition that started and ended prior to Screening. Concomitant disease is defined as any condition that was ongoing at Screening.

Medical history and concomitant disease will be coded using Medical Dictionary for Regulatory Activities (MedDRA) version 16.0 or later and listed separately by randomization arm, System Organ Class (SOC) and Preferred Term (PT) within SOC.

Medical History and concomitant disease will be summarized by randomization arm, SOC and PT for the Safety Population.

The data will be presented in the below outputs:

TFL number	Title
TABLES	
15.2.1.6.1	Summary of Medical History – Safety Population
15.2.1.7.1	Summary of Concomitant Diseases– Safety Population
LISTINGS	
15.3.1.10	Listing of Medical History and Concomitant Diseases

12.3.4 Other Data

Other data collected at Screening and/or Admission will be listed by randomization arm. These data are as follows:

- Cotinine urine test.
- Urine pregnancy test.
- Chest x-ray.
- Urine drug screen.
- Serology (excluding HIV status).
- Alcohol breath test.

- Prior medication.
- Willingness to use THS 2.2 Menthol products.
- Product preference question.

Prior Medication will be summarized as described in Section 12.6.4.4.1 “Prior and Concomitant Medication”.

Product preference will be collected at Admission (Day -2) and states the product which the subject prefers to be randomized to (THS 2.2 Menthol, mCC, SA or No preference). Data will be summarized by randomization arms along with Baseline characteristics. Willingness and ability to use the product will be included in the disposition summary table for all screened subjects.

The data will be presented in the below outputs:

TFL number	Title
TABLES	
15.2.1.1	Summary of Subject Disposition – All Screened Subjects
15.2.6.19.1	Summary of Prior Medication by Anatomical Therapeutic Classes (ATC) 1 and 2 – Safety Population
15.2.6.19.2	Summary of Prior Medication by Preferred Term – Safety Population
LISTINGS	
15.3.1.4	Listing of Product Test and Willingness to Use the Product
15.3.1.6	Listing of Product Preference
15.3.1.7	Listing of Safety Laboratory Entry Criteria
15.3.6.3	Listing of Prior and Concomitant Medication

12.4 Measurements of Product Compliance

From Day -2 onwards during the confinement period, each mCC will be dispensed to the subjects one by one. Subjects in the THS 2.2 Menthol arm will be provided by the site study collaborators with Menthol Tobacco Sticks from Day 1 to Day 5 stick by stick. One mCC/Menthol Tobacco Stick will be allowed at a time.

Levels of CO in exhaled breath will be measured in the SA arm to ensure that the subjects have not smoked any cigarettes. This will serve as a compliance tool starting from Day 2, because of possible carry over effect. These data (continuous and categorical) will be summarized and listed by product use category (Table 20) in the SA arm.

During the ambulatory period, subjects in the 3 study arms will capture, from the time of Discharge on Day 6 to Day 90, the number of product used (e.g., menthol and non-menthol CC, Menthol Tobacco Sticks, or any other tobacco /nicotine-containing products including NRT) on a daily basis in the product use electronic diary. The product use electronic diary will serve as a compliance tool in the 3 arms. On Day 6, the compliance to the product will be ensured using both the accountability log (from 06:30 AM to time

of discharge) and the product use electronic diary (filled from the time of Discharge on Day 6 to Day 90).

The data will be presented in the below outputs:

TFL number	Title
TABLES	
15.2.5.1	Summary of Compliance as Measured by Exhaled CO (ppm) in the SA Arm During Confinement Period- FAS
15.2.5.2	Summary of Compliance by Period - FAS
LISTINGS	
15.3.3.2	Listing of Secondary Biomarkers
15.3.2.1	Listing of Product Usage

12.5 Extent of Exposure (Product Consumption)

Details of the product test prior to enrollment and of product use after randomization will be listed and summarized. During the confinement period the daily usage, as recorded in the log, will be summarized by randomization arm.

The maximum and average daily usage of the assigned product and non-assigned product will be summarized over the whole ambulatory period, as recorded by the subject, and for each of the periods 2 to 4 (see section 10.2 “Per Protocol Set”).

All summaries will be produced for the Safety Population, and for the PP Set at periods 1 to 4. Summaries of data in Ambulatory will also be repeated for the FAS, if the population differs from the Safety population by more than 10%.

In addition the number and percentage of subjects falling into each product use category (see Section 6.3.3.1 “Dual-use”) during the ambulatory period will be presented.

The average product use data will also be presented by randomized product and by product use categorization (see Section 6.3.3.1 “Dual-use”).

The data will be presented in the below outputs:

TFL number	Title
TABLES	
15.2.2.1.1	Summary of Daily Product Use in Confinement Period – Safety Population
15.2.2.1.2	Summary of Daily Product Use in Confinement Period – FAS
15.2.2.1.3	Summary of Daily Product Use in Confinement Period – PP Set
15.2.2.2.1	Summary of Maximum Daily Product Use in Ambulatory Period– Safety Population
15.2.2.2.2	Summary of Maximum Daily Product Use in Ambulatory Period– FAS

TFL number	Title
15.2.2.2.3	Summary of Maximum Daily Product Use in Ambulatory Period– PP Set
15.2.2.3.1	Summary of Average Daily Product Use in Ambulatory Period– Safety Population
15.2.2.3.2	Summary of Average Daily Product Use in Ambulatory Period – FAS
15.2.2.3.3	Summary of Average Daily Product Use in Ambulatory Period – PP Set
15.2.2.4.1	Summary of Product Use by Product Use Category in Ambulatory Period – Safety Population
15.2.2.4.2	Summary of Product Use Category in Ambulatory Period – FAS
15.2.2.4.3	Summary of Product Use Category in Ambulatory Period – PP Set
15.2.2.5.1	Summary of Average Daily Product Use by Product Use Category in Ambulatory Period – Safety Population
15.2.2.5.2	Summary of Average Daily Product Use by Product Use Category in Ambulatory Period – FAS
15.2.2.5.3	Summary of Average Daily Product Use by Product Use Category in Ambulatory Period – PP Set
LISTINGS	
15.3.2.1	Listing of Product Usage
15.3.2.2	Listing of Cigarette Butt and THS Menthol Tobacco Stick Collection Data

12.6 Planned Statistical Analyses

For all statistical analysis data from all arms, THS 2.2 Menthol, mCC and SA will be included in all models as appropriate.

12.6.1 Primary Analyses

12.6.1.1 Analysis of Biomarkers of Exposure for Primary Objectives

The BoExp (COHb in blood and urinary concentrations of MHBMA, 3-HPMA, S-PMA and Total NNAL) used for the primary analysis will be described as detailed in Section 12.1.3 “Descriptive Statistics”. The listing of the COHb data will have a flag for whether a subject’s COHb was <2%.

The baseline is as defined in Section 12.1.4 “Definitions for Statistical Data Analysis”.

The primary endpoints will be log-transformed (base_e) prior to analysis. The analysis will compare the evening COHb level (20:00-21:30) at Day 5; and urinary concentrations of MHBMA, 3-HPMA and S-PMA adjusted for creatinine on Day 5 and urinary concentrations of Total NNAL adjusted for creatinine on Day 90 Visit between the THS 2.2 Menthol and mCC arms for the PP Set. An analysis of covariance (ANCOVA) (Snedecor and Cochran 1982) model will be used with terms for the log-transformed baseline value, sex, average daily mCC consumption over the last 4 weeks as reported during screening and randomization arm.

The SAS code to be used for the THS 2.2 Menthol and mCC data is shown below:

```
Proc glm data=_data_ ;
  Class randomization_arm sex cigarette_cons;
  Model log_biomarker = log_baseline sex cigarette_cons
    randomization_arm;
  Lsmean randomization_arm / pdiff =control('mCC') alpha=0.05 cl;
  Run;
```

The least squares (LS) means and estimate of the difference and the 95% CI will be back-transformed. The geometric LS means for each randomization arm along with the ratio (THS 2.2 Menthol : mCC), two-sided 95% CI and one-sided p-value will be presented in the tables. THS 2.2 Menthol : CC effects will be graphed in a forest plot.

All figures, summaries and analyses will be performed on the PP Set. Additional descriptive statistics will be provided within the secondary analysis.

The data will be presented in the below outputs:

TFL number	Title
FIGURES	
15.1.1.1	Forest Plots of Statistical Analysis of Biomarkers of Exposure for Primary Objective – PP Set
15.1.1.2	Biomarker of Exposure for Primary Objective Arithmetic Mean and 95% CI for Percent Change from Baseline – PP Set
TABLES	
15.2.3.1.1	Analysis of COHb, MHBMA, 3-HPMA, S-PMA and Total NNAL on Day 5/90 Visit for THS 2.2 Menthol versus mCC for the Primary Objective – PP Set
15.2.4.1.1	Descriptive Statistics of Blood COHb (%) – PP Set
15.2.4.1.1.1	Descriptive Statistics of Blood COHb (%) by Sex – PP Set
15.2.4.1.1.2	Descriptive Statistics of Blood COHb (%) by Cigarette Consumption – PP Set
15.2.4.2.1	Descriptive Statistics of MHBMA in 24-hour Urine Collection – PP Set
15.2.4.2.1.1	Descriptive Statistics of MHBMA Urinary Concentration Adjusted for Creatinine (units) in 24-hour Urine Collection by Sex – PP Set
15.2.4.2.1.2	Descriptive Statistics of MHBMA Urinary Concentration Adjusted for Creatinine (units) in 24-hour Urine Collection by Cigarette Consumption – PP Set
15.2.4.3.1	Descriptive Statistics of 3-HPMA in 24-hour Urine Collection – PP Set
15.2.4.3.1.1	Descriptive Statistics of 3-HPMA Urinary Concentration Adjusted for Creatinine (units) in 24-hour Urine Collection by Sex – PP Set

TFL number	Title
15.2.4.3.1.2	Descriptive Statistics of 3-HPMA Urinary Concentration Adjusted for Creatinine (units) in 24-hour Urine Collection by Cigarette Consumption – PP Set
15.2.4.4.1	Descriptive Statistics of S-PMA in 24-hour Urine Collection – PP Set
15.2.4.4.1.1	Descriptive Statistics of S-PMA Urinary Concentration Adjusted for Creatinine (units) in 24-hour Urine Collection by Sex – PP Set
15.2.4.4.1.2	Descriptive Statistics of S-PMA Urinary Concentration Adjusted for Creatinine (units) in 24-hour Urine Collection by Cigarette Consumption – PP Set
15.2.4.5.1	Descriptive Statistics of Total NNAL in 24-hour Urine Collection – PP Set
15.2.4.5.1.1	Descriptive Statistics of Total NNAL Urinary Concentration Adjusted for Creatinine (units) in 24-hour Urine Collection by Sex – PP Set
15.2.4.5.1.2	Descriptive Statistics of Total NNAL Urinary Concentration Adjusted for Creatinine (units) in 24-hour Urine Collection by Cigarette Consumption – PP Set
LISTINGS	
15.3.3.1.1	Listing of Biomarkers of Exposure COHb and CO.
15.3.3.1.2	Listing of Biomarkers of Exposure MHBMA and 3-HPMA.
15.3.3.1.3	Listing of Biomarkers of Exposure S-PMA and Total NNAL..

12.6.1.2 Confirmatory Analysis

The hypothesis to be tested is that the geometric mean level of the BoExp for THS 2.2 Menthol is lower relative to mCC and will be as described in Section 12.6.1.1 "Analysis of Biomarkers of Exposure for Primary Objectives".

12.6.1.3 Sensitivity Analysis

As a sensitivity analysis, the ANCOVA model described in Section 12.6.1.1 "Analysis of Biomarkers of Exposure for Primary Objectives" will be repeated for the PP Set at Day 5 and Day 90 data by means of a mixed model approach, without the LOCF data imputation described in Section 12.1.5 "Handling of Dropouts or Missing Data (including outside the limits of quantification)". Any data outside of the allowed time window (see Table 18: Assessment Windows) on Days 5 and 90 will be excluded from the analysis.

The SAS code to be used for the THS 2.2 Menthol and mCC data is shown below:

```
Proc mixed data=_data_;
  Class randomization_arm sex cigarette_cons;
  Model log_biomarker = log_baseline sex cigarette_cons
    randomization_arm;
  Lsmean randomization_arm / pdiff =control('mCC') alpha=0.05 cl;
  Run;
```

An additional sensitivity analysis will be produced for the primary analysis, summaries and graphs of the COHb, MHBMA, 3-HPMA, S-PMA and Total NNAL will be repeated for the compliant population for THS 2.2 Menthol vs mCC. The analysis will use the same model as described in Section 12.6.1.1 "Analysis of Biomarkers of Exposure for Primary Objectives"

The data will be presented in the below outputs:

TFL number	Title
FIGURES	
15.1.1.3	Biomarker of Exposure Arithmetic Mean and 95% CI for Percent Change from Baseline – Compliant Population
TABLES	
15.2.3.1.2	Sensitivity Analysis of COHb, MHBMA, 3-HPMA, S-PMA and Total NNAL on Day 5/90 Visit for THS 2.2 Menthol versus mCC for the Primary Objective using Mixed Model – PP Set
15.2.3.1.3	Sensitivity Analysis of COHb, MHBMA, 3-HPMA, S-PMA and Total NNAL on Day 5/90 Visit for THS 2.2 Menthol versus mCC for the Primary Objective – Compliant Population
15.2.4.1.3	Descriptive Statistics of Blood COHb (%) – Compliant Population
15.2.4.2.3	Descriptive Statistics of MHBMA in 24-hour Urine Collection – Compliant Population
15.2.4.3.3	Descriptive Statistics of 3-HPMA in 24-hour Urine Collection – Compliant Population
15.2.4.4.3	Descriptive Statistics of S-PMA in 24-hour Urine Collection – Compliant Population
15.2.4.5.3	Descriptive Statistics of Total NNAL in 24-hour Urine Collection – Compliant Population

12.6.2 Secondary Analyses

The analysis of COHb, MHBMA, 3-HPMA, and S-PMA at Day 90 and Total NNAL at Day 5 will be repeated for the PP Set.

The analysis of the COHb, MHBMA, 3-HPMA, S-PMA at Day 5/ Day 90 and Total NNAL at Day 90 will be repeated for the FAS as described in Section 12.6.1.1 "Analysis of Biomarkers of Exposure for Primary Objectives". These endpoints will also be

examined to compare the reductions in THS 2.2 Menthol vs. SA using the same methodology as for the primary analysis for the PP Set.

The baseline is for the biomarkers measured in urine is as defined in Section 12.1.4 "Definitions for Statistical Data Analysis".

12.6.2.1 Analysis of Biomarkers of Exposure for Secondary Objectives

The BoExp for the secondary objectives are exhaled CO and total 1-OHP, Total NNN, 4-ABP, 1-NA, 2-NA, o-tol, CEMA, HEMA, B[a]P, HMPMA, S-BMA and NEQ (all analysed from a 24-hour urine collection) at Day 5 and Day 90 will be described as reported in Section 12.1.3 "Descriptive Statistics". Urine parameters will be analyzed as concentration adjusted for creatinine and the quantity excreted in urine over 24 hours. In addition the quantity excreted in urine over 24 hours for MHBMA, 3-HPMA, S-PMA and Total NNAL will also be presented as above.

All BoExp apart from CO breath test will be analyzed in the log scale.

BoExp will be analyzed using the same model described in Section 12.6.1.1 "Analysis of Biomarkers of Exposure for Primary Objectives". No adjustment will be made for multiple comparisons. For all BoExp, if the results from the Day 5 analysis are significant (one-sided p-value ≤ 0.025) then the statistical significance will be evaluated for the results of the analysis at Day 90 values. LS means for each product along with the ratio (THS 2.2 Menthol : mCC) and 95% CI will be presented in the tables. Forest plots of the ratios and 95% CI will also be produced.

BoExp will also be examined to compare the reductions in THS 2.2 Menthol vs. SA using the same methodology as above for the PP Set. In addition, the sensitivity analyses described in Section 12.6.1.3 "Sensitivity Analysis" for the biomarkers of exposure for primary objectives will be repeated for the biomarkers of exposure for secondary objectives.

The data will be presented in the below outputs:

TFL number	Title
FIGURES	
15.1.1.2	Biomarker of Exposure Arithmetic Mean and 95% CI for Percent Change from Baseline – PP Set
15.1.1.4	Biomarker of Exposure Arithmetic Mean and 95% CI for Percent Change from Baseline – FAS
15.1.1.5	Forest Plots of Statistical Analysis of Biomarkers of Exposure for Secondary Objective – PP Set
TABLES	
15.2.3.2	Analysis of COHb, MHBMA, 3-HPMA, S-PMA, and Total NNAL on Day 5/90 Visit versus mCC and SA for the Secondary Objective – PP Set.

TFL number	Title
15.2.3.3	Analysis of COHb, MHBMA, 3-HPMA, S-PMA, and Total NNAL on Day 5/90 Visit versus mCC and SA for the Secondary Objective – FAS.
15.2.3.4	Analysis of Additional Biomarkers of Exposure versus mCC and SA on Day 5/90 Visit– PP Set.
15.2.3.5	Analysis of Additional Biomarkers of Exposure versus mCC and SA on Day 5/90 Visit– FAS.
15.2.3.6	Analysis of Additional Biomarkers of Exposure versus mCC and SA using Mixed Model on Day 5/90 Visit – PP Set
15.2.3.7	Analysis of Additional Biomarkers of Exposure versus mCC and SA on Day 5/90 Visit– Compliant Population
15.2.4.1.2	Descriptive Statistics of Blood COHb (%) – FAS
15.2.4.1.3	Descriptive Statistics of Blood COHb (%) – Compliant Population
15.2.4.2.2	Descriptive Statistics of MHBMA in 24-hour Urine Collection – FAS
15.2.4.2.3	Descriptive Statistics of MHBMA in 24-hour Urine Collection – Compliant Population
15.2.4.3.2	Descriptive Statistics of 3-HPMA in 24-hour Urine Collection – FAS
15.2.4.3.3	Descriptive Statistics of 3-HPMA in 24-hour Urine Collection – Compliant Population
15.2.4.4.2	Descriptive Statistics of S-PMA in 24-hour Urine Collection – FAS
15.2.4.4.3	Descriptive Statistics of S-PMA in 24-hour Urine Collection – Compliant Population
15.2.4.5.2	Descriptive Statistics of Total NNAL in 24-hour Urine Collection – FAS
15.2.4.5.3	Descriptive Statistics of Total NNAL in 24-hour Urine Collection – Compliant Population
15.2.4.6.1	Descriptive Statistics of Exhaled CO (ppm) – PP Set
15.2.4.6.2	Descriptive Statistics of Exhaled CO (ppm) – FAS
15.2.4.7.1	Descriptive Statistics of 1-OHP in 24-hour Urine Collection – PP Set
15.2.4.7.2	Descriptive Statistics of 1-OHP in 24-hour Urine Collection – FAS
15.2.4.8.1	Descriptive Statistics of Total NNN in 24-hour Urine Collection – PP Set
15.2.4.8.2	Descriptive Statistics of Total NNN in 24-hour Urine Collection – FAS
15.2.4.9.1	Descriptive Statistics of 4-ABP in 24-hour Urine Collection – PP Set
15.2.4.9.2	Descriptive Statistics of 4-ABP in 24-hour Urine Collection – FAS
15.2.4.10.1	Descriptive Statistics of 1-NA in 24-hour Urine Collection – PP Set
15.2.4.10.2	Descriptive Statistics of 1-NA in 24-hour Urine Collection – FAS
15.2.4.11.1	Descriptive Statistics of 2-NA in 24-hour Urine Collection – PP Set
15.2.4.11.2	Descriptive Statistics of 2-NA in 24-hour Urine Collection – FAS
15.2.4.12.1	Descriptive Statistics of o-tol in 24-hour Urine Collection – PP Set
15.2.4.12.2	Descriptive Statistics of o-tol in 24-hour Urine Collection – FAS
15.2.4.13.1	Descriptive Statistics of CEMA in 24-hour Urine Collection – PP Set
15.2.4.13.2	Descriptive Statistics of CEMA in 24-hour Urine Collection – FAS
15.2.4.14.1	Descriptive Statistics of HEMA in 24-hour Urine Collection – PP Set
15.2.4.14.2	Descriptive Statistics of HEMA in 24-hour Urine Collection – FAS
15.2.4.15.1	Descriptive Statistics of B[a]P in 24-hour Urine Collection – PP Set

TFL number	Title
15.2.4.15.2	Descriptive Statistics of B[a]P in 24-hour Urine Collection – FAS
15.2.4.16.1	Descriptive Statistics of HMPMA in 24-hour Urine Collection – PP Set
15.2.4.16.2	Descriptive Statistics of HMPMA in 24-hour Urine Collection – FAS
15.2.4.17.1	Descriptive Statistics of S-BMA in 24-hour Urine Collection – PP Set
15.2.4.17.2	Descriptive Statistics of S-BMA in 24-hour Urine Collection – FAS
15.2.4.18.1	Descriptive Statistics of NEQ in 24-hour Urine Collection – PP Set
15.2.4.18.2	Descriptive Statistics of NEQ in 24-hour Urine Collection – FAS
LISTINGS	
15.3..3.2.1	Listing of Biomarkers of Exposure (total 1-OHP and total NNN)
15.3.3.2.2	Listing of Biomarkers of Exposure (4-ABP and 1-NA)
15.3.3.2.3	Listing of Biomarkers of Exposure (2-NA and o-tol)
15.3.3.2.4	Listing of Biomarkers of Exposure (CEMA and HEMA)
15.3.3.2.5	Listing of Biomarkers of Exposure (B[a]P and HMPMA)
15.3.3.2.6	Listing of Biomarkers of Exposure (S-BMA and NEQ)

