lowering (Ashley et al., 2008). Exposure to 4 HPHCs (acrolein, CO, 1,3-butadiene, and benzene) among these nine priority HPHCs will be assessed by measuring their respective BoExp as primary endpoints after 5 days of exclusive use of THS 2.2 Menthol, mCC or SA. The following characteristics apply to these primary BoExp:

- They are several-fold higher in smokers than in smokers abstinent from smoking (Lindner et al., 2011).
- They exhibit, on average, an elimination half-life of \leq 24 hours. Therefore, the 5 days of exposure are sufficient to reach the steady state with the THS 2.2 Menthol and SA arms (4 to 5 times the half-life will lead to less than 5% of the original exposure levels of assessed biomarkers on Day 5).
- They were decreased in smokers who switched to another candidate MRTP tested in exploratory studies for 5 days, similar to that observed in smokers who stopped smoking (data on file from the previous study, YVD-CS01-EU study).

Total NNAL was selected as primary endpoints after 90 days of THS 2.2 Menthol use as:

- This biomarker is tobacco specific (Goniewicz et al., 2009), and exhibits, on average, an elimination half-life of 10 to 15 days. Therefore, the 90 days of exposure are sufficient to reach the steady state with the THS 2.2 Menthol and SA arms (4 to 5 times the half-life will lead to less than 5% of the original exposure levels on Day 90 Visit).
- It was decreased in smokers who switched to another candidate MRTP after 5 days, (data on file from the previous study, YVD-CS01-EU study).

In addition, some risk markers have been selected in order to evaluate biological changes in THS 2.2 Menthol arm as compared to mCC arm using SA arm as a reference point to verify if the trend of changes upon THS 2.2 Menthol use follow the same trajectory as SA. Among the ones selected, some well-known to be affected by smoking and to be reversible upon SA, will be measured in this study as follows:

1. CYP1A2 activity, the enzyme which mainly metabolizes nicotine, is decreased as soon as 5 days of smoking abstinence and after 5 days of use of another candidate MRTP (Faber et al., 2004) and data on file from a previous study [YVD-CS01-EU study].
2. Platelet function will be assessed by measuring 11-DTX-B2 (a major stable metabolite of thromboxane A2, which elicits mainly platelet aggregation). This marker was decreased after 1 week of SA (Benowitz et al., 1993) and after 5 days of use of another candidate MRTP (YVD-CS01-EU study).

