12.6.4 Inferential Analysis

For the secondary BoExp and selected risk markers, the hypothesis to be tested is the same as described in Section 12.5.4. This will be tested for secondary BoExp on Day 5, and if significant, on Day 90 (except Total NNAL).

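### SAP 12.6.2.1 omits the protocol's Total NNAL exception, so the Day 90 significance statement for NNAL quantity excreted can depend on a Day 5 test made well before steady state

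*SAP*

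**What the plan says.** - **Protocol 4.2** places Total NNAL at Day 90 because it "exhibits, on average, an elimination half-life of 10 to 15 days". The four Day 5 primary markers are there because their half-lives are 24 hours or less.
- **Protocol 12.6.4** sets the sequence for secondary BoExp and carves out one marker: "This will be tested for secondary BoExp on Day 5, and if significant, on Day 90 (except Total NNAL" (the bracket closes there).
- **SAP 12.6.2.1** first covers the secondary biomarkers, with urine parameters analysed both as creatinine-adjusted concentration and as quantity excreted. It then adds that "the quantity excreted in urine over 24 hours for MHBMA, 3-HPMA, S-PMA and Total NNAL will also be presented as above". The gate follows, at one-sided p ≤ 0.025: "For all BoExp, if the results from the Day 5 analysis are significant". It names no exception.
- **SAP 12.6.2** also schedules a Day 5 analysis of the creatinine-adjusted marker: "Total NNAL at Day 5 will be repeated for the PP Set".
- **SAP 5.2** points the other way on scope. Under the objective to determine reduction (objective 2) it lists quantity excreted for MHBMA, S-PMA and 3-HPMA by name, but not for Total NNAL. Total NNAL quantity excreted appears only under objective 3, which is descriptive.
- **SAP Section 9**, the list of changes from the protocol, is silent on this. It does record changes as small as a preposition in the creatinine wording.

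**The concern.** A Day 5 gate suits markers that are at steady state by Day 5. Total NNAL is the one marker for which the protocol argues the opposite. The Day 5 collection runs from the fourth to the fifth day after the switch, at most half of one half-life, so most of what is measured comes from smoking before randomization. A Day 5 test can therefore miss significance because washout is incomplete, even when the steady-state reduction is as large as the plan expects.

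At stake is whether a Day 90 significance statement is made for Total NNAL quantity excreted. The same marker, from the same Day 90 urine, could carry a p-value in creatinine-adjusted units and none as quantity excreted, for a reason unrelated to the Day 90 data. There is also a traceability problem, because the protocol and SAP rules differ and the difference is undeclared.

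**Working it through.** **Inputs.** Half-life h of 10 to 15 days (Protocol 4.2). Exposure starts on Day 1 at 06:30, and the Day 5 urine runs from 06:30 on Day 5 to 06:29 on Day 6 (Protocol 7.7.2), so t = 4 to 5 days after the switch. Expected Total NNAL ratio 0.30 with CV 0.60 (Protocol Table 20, SAP Table 12). Sample sizes 80:40 on Day 5 and 40:40 for Total NNAL on Day 90 (SAP Table 14). One-sided alpha 0.025. The hypothesis is a ratio below 1.

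**Assumed, because the documents do not give them.** The CV of quantity excreted, and of Total NNAL on Day 5, is taken as 0.60. The correlation rho between log baseline and log Day 5 value is varied from 0 to 0.9. Decay is taken as one-compartment.

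**1. Reproducing the plan's figures.** SD on the log scale = √ln(1 + CV²). The shift is ln(MR/0.5), power comes from the noncentral t, and the five powers are multiplied. For Total NNAL, SD = √ln(1.36) = 0.5545 and power at 40:40 is 0.983.
- YVD-CS01-EU inputs: COHb 0.956, the other three about 1.000, product 0.939 (plan: 94%).
- ZRHX-EX-01 inputs: COHb 0.997, the other three about 1.000, product 0.979 (plan: 98%).

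The protocol's Day 90 washout statement also holds: 2^(−90/10) = 0.2% and 2^(−90/15) = 1.6%, both under 5%.

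**2. Residual pre-switch NNAL in the Day 5 urine.** The mean of 2^(−t/h) over t = 4 to 5 is (h/ln 2) × [2^(−4/h) − 2^(−5/h)].
- h = 10: 14.427 × (0.7579 − 0.7071) = 0.732
- h = 15: 21.640 × (0.8312 − 0.7937) = 0.812

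**3. Expected Day 5 ratio.** If intake falls at once to the level that gives 0.30 at steady state, ratio = 0.30 + 0.70 × residual.
- h = 10: 0.30 + 0.70 × 0.732 = 0.81
- h = 15: 0.30 + 0.70 × 0.812 = 0.87

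**4. Probability that the gate opens.** SE = 0.5545 × √(1 − rho²) × √(1/80 + 1/40), which is 0.1074 at rho = 0. The noncentrality is −ln(ratio)/SE, which at rho = 0 is 0.2076/0.1074 = 1.93 (10 days) and 0.1408/0.1074 = 1.31 (15 days).

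| rho (assumed) | 10-day half-life | 15-day half-life |
|---|---|---|
| 0 | 48.3% | 25.5% |
| 0.5 | 60.0% | 32.4% |
| 0.7 | 76.6% | 44.5% |
| 0.8 | 89.2% | 58.2% |
| 0.9 | 99.3% | 84.7% |

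If NNK intake fell to zero, which is more favourable than the plan's 0.30, the ratio would equal the residual and the rho = 0 figures would be 82% and 48%.

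**5. The ungated Day 90 test.** At ratio 0.30 and 40:40, SE = 0.5545 × √(1/40 + 1/40) = 0.124, noncentrality = 1.204/0.124 = 9.7, and power exceeds 99.9%.

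**The case against.** The case on the other side has four parts, and much of it stands.

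1. **The gated test may not exist.** SAP 5.2 puts Total NNAL quantity excreted under a descriptive objective, and the SAP 12.6.2.1 sentence says it will be presented, which can be read as summaries only. This stands as an ambiguity. It does not remove the problem, because the gate sentence says all BoExp and the section says urine parameters are analysed in both units.
2. **The protocol exception may mean less.** Total NNAL is a primary marker, so Protocol 12.6.4 may only be saying that it is handled elsewhere. That is possible. On either reading the protocol does not make a Day 90 Total NNAL test conditional on Day 5, and the SAP wording does.
3. **Little is lost.** This stands. The SAP 12.6.1.1 primary test is ungated. SAP 12.6.2.1 presents the ratio and 95% CI without tying them to the gate, and a two-sided 95% CI that lies wholly below 1 gives the same conclusion as the one-sided 2.5% test.
4. **The low probabilities ignore the baseline covariate.** This stands. The planned model adjusts for log baseline, and if most Day 5 NNAL is carry-over, a substantial correlation is plausible. The table therefore runs to rho = 0.9, and the rho = 0 row should not be quoted alone.

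A reader might go further and infer that NNAL shows no effect by Day 5, or that the Day 5 NNAL result should be suppressed. The documents do not support either. Protocol 4.2 itself reports a decrease after 5 days with another candidate product (no size given), and the calculation above gives a 13% to 19% reduction, which is attenuated but present. The Day 5 contrast is a valid randomized comparison short of steady state, so withholding its p-value would be a preference.

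**Conclusion.** The point holds in a limited form. As written, SAP 12.6.2.1 makes the Day 90 significance of Total NNAL quantity excreted conditional on Day 5. Protocol 12.6.4 excepts Total NNAL from that rule, SAP Section 9 does not declare the difference, and SAP 5.2 leaves it unclear whether the quantity is tested at all.

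Under the plan's half-life and expected ratio, the chance that the gate opens lies between about 26% and 99%, depending on half-life (10 to 15 days) and baseline correlation (0 to 0.9). The Day 90 test that it controls has power above 99.9%. That range rests on a CV borrowed from the Day 90 planning figure, an assumed correlation and one-compartment decay. The direction of the effect follows from the protocol's own kinetics; the size within the range cannot be settled from the documents.

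It would be wrong to conclude that the primary NNAL objective, or the reporting of the Day 90 reduction, is at risk. The effect is confined to one secondary significance statement.

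**What to change.** - **SAP 12.6.2.1:** insert *except Total NNAL* after the words all BoExp in the gate sentence, so that any Day 90 test of Total NNAL quantity excreted does not depend on Day 5.
- **SAP 5.2:** state whether Total NNAL quantity excreted is tested or only described, so that it agrees with 12.6.2.1.
- **SAP Section 9:** list any remaining departure from Protocol 12.6.4.
- **Day 5 Total NNAL:** keep the analysis. A footnote that Day 5 precedes steady state for this marker is optional.

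The cost is one clause and one or two lines of alignment, with no new data or analysis. SAP 12.1.7 makes no multiplicity adjustment for secondary endpoints, so lifting the condition for one of them weakens no controlled error rate. If the SAP can no longer be amended, the clinical study report can record the change, as SAP Section 3 provides.
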